7.4 Withdrawal of individual subjects

Subjects can leave the study at any time for any reason without any consequences. The investigator can decide to withdraw a subject from the study for urgent medical reasons.

7.5 Replacement of individual subjects after withdrawal

Subjects who are withdrawn during the study will not be replaced.

7.6 Follow-up of subjects withdrawn from the study

Subjects who are withdrawn will continue to receive normal, standard of care follow-up by the study physician.

7.7 Premature termination of the study

The Post Market pilot Study will be terminated prematurely if the Investigators feel there is a risk to the subjects enrolled. Subject safety will continue to be monitored by the Investigators for the duration of the device.

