6.2 Summary of known and potential risks and benefits of the therapy

A summary of the known and potential risks and benefits can be found in the accompanying manuals that are included in the package of the components. The general risks associated with the Spinal Modulation Neurostimulator System are similar to those associated with other Spinal Cord Stimulator systems. Possible risks to the subjects include both device and procedural based risks.

The most common side effects and risks are:

- Pain (where the needle is to be inserted)
- Pain caused by under stimulation due to lead migration
- Pain over the implantable neurostimulator site (only applicable in Phase 2)
- Escalating pain
- Bleeding (where the needle has been inserted)
- Headache
- Infection
- Localized collection of serous (clear) fluid at injection site
- Discomfort during the treatment
- Allergic or rejection response to implant materials
- Constant pain at the lead site
- Stimulation of the chest wall
- Lead migration (movement) and/or local skin breakage
- Weakness
- Clumsiness
- Numbness
- Temporary muscle activation

Very rare risks and side effects include:

- Cerebral Spinal Fluid (CSF) leakage
- Tissue damage
- Nerve damage
- Spinal cord compression
- Swelling
- Paralysis
- Hematoma
- Seroma
- Sensory loss
- Skin erosion around the INS or leads
- Battery failure and/or battery leakage
- Lead breakage requiring replacement of the lead
- Hardware malfunction requiring replacement of the neurostimulator
- Pain from a non-injurious stimulus to the skin (allodynia)
- An exaggerated sense of pain (hyperesthesia)

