7.2 Randomisation, blinding and treatment allocation

As this is a single-arm observational study, no randomisation or blinding will occur. All eligible subjects recruited into the study will undergo treatment in the usual manner and complete questionnaires at routinely scheduled follow up appointments. Subject who decided not to take part in this study will not receive a neurostimulator and will be monitored by their physician as needed in accordance with standard medical procedures.

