8 SAFETY REPORTING

8.1 Applicable local laws and regulations

For the reporting of events in this trial, applicable international standards and guidance documents for CE marked products will be followed (AIMDD, MEDDEV 2.12/2 rev2 and MEDDEV 2.12-1 rev 8), the applicable local laws and regulations, and the SMI/SJM internal operating procedures on complaint reporting, whichever is the most stringent.

In this regard investigators will only need to report device related Adverse Events (AE) and device related Serious Adverse Events (SAE).

Additionally, all reported device related AEs and SAEs will be reviewed internally at Spinal Modulation Inc./St. Jude Medical according to the criteria for incidents to be reported by manufacturers to competent authorities, as defined in section 5.1.1 in the MEDDEV 2.12-1 Rev 8.

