8.5 Data Safety Monitoring Board (DSMB)

This post market pilot study is purely observational using a routinely utilised therapy within its licensed indications. According to the DSMB risk classification ('Kwaliteitsborging mensgebondenonderzoek 2.0', from www.NFU.nl on 13th May 2014) this study represents negligible risk to participants and therefore a DSMB will not be necessary for this study.

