10.4 Compensation for injury

The implantation of the system is a standard procedure in the hospital and regular follow up visits for the first year after this procedure are also standard practice. While this procedure is not routinely offered to patients with Discogenic low back pain due to reimbursement restrictions, the use of the therapy in this patient group falls within the CE mark indication for the treatment. As participants in this research would not be offered this therapy if they would not be enrolled in this study, a clinical trial insurance is in place to reassure coverage in case of any complications.

In addition, the sponsor/investigator has a liability insurance that provides cover for damage to subjects through injury or death caused by the use of the device

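### Section 8.5's grounds for waiving the DSMB conflict with the protocol's own account of why subjects are implanted, and 7.7 leaves termination to undefined judgement with no documented route for pooled events to reach the investigators

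*Combined protocol and SAP*

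**What the plan says.** Section 7.7 gives the only early-termination criterion in the readable text: "The Post Market pilot Study will be terminated prematurely if the Investigators feel there is a risk to the subjects enrolled". It names no event type, number of events, data source, review time, or procedure if the centres disagree.

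Section 8.5 explains why there is no independent board. It says "This post market pilot study is purely observational using a routinely utilised therapy within its licensed indications" and, citing an external risk classification, concludes that "this study represents negligible risk to participants and therefore a DSMB will not be necessary for this study".

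Section 10.4 describes the same treatment differently: "While this procedure is not routinely offered to patients with Discogenic low back pain due to reimbursement restrictions", and "As participants in this research would not be offered this therapy if they would not be enrolled in this study", which is the reason given for holding clinical trial insurance. The Summary (Risks) says the same. Section 7.2 adds: "Subject who decided not to take part in this study will not receive a neurostimulator"; section 3 agrees.

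Section 6.2 states that risks are both device-based and procedural. Infection and lead migration are among the most common. Nerve damage, paralysis and "Spinal cord compression" are in the list of very rare ones.

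Under 8.1, investigators need report only device-related AEs and SAEs, and "all reported device related AEs and SAEs will be reviewed internally" by the sponsor, using the criteria for incidents that manufacturers must report to competent authorities. Section 8.3 asks for timely documentation without a number of days.

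**The concern.** Two things do not fit together.

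First, a study in which enrolment causes the surgery is not observational in the sense that would justify lighter safety oversight. Subjects take on a two-stage epidural lead and stimulator implantation that they would not otherwise be offered. The grounds in 8.5 do not acknowledge this.

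Second, once the board is waived, the decision to stop lies with the investigators, and 7.7 gives them nothing to apply. Because 6.2 lists risks before anyone is enrolled, the existence of a risk cannot separate expected events from unacceptable ones. The study is multi-centre, and the body that receives all reported events is the sponsor. No section connects the sponsor's review in 8.1 to the decision in 7.7.

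At stake is whether those empowered to stop would be working from the whole of a very small data set or from their own part of it.

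**Working it through.** **Consistency check.** There is no stated stopping boundary or safety threshold to reproduce, and 4.4 says no formal sample size estimation was made. The main check sets sections side by side.

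| Ground in 8.5 | Text elsewhere | Result |
|---|---|---|
| Purely observational | Summary, 3, 7.2, 10.4: the implant is received only through enrolment | Conflict |
| Negligible risk | Summary, 10.4: trial insurance held because the therapy would not otherwise be offered; 6.2: device and procedural risks | Sits badly; must be reconciled |
| Routinely utilised therapy | 10.4: not routinely offered to these patients, for reimbursement reasons; implantation itself is standard in the hospital | Weak conflict; the phrase can describe the therapy in general |

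**Tracing an event.** An event goes from the site CRF to the sponsor (8.3), then to sponsor review for reportability (8.1), then to the authorities if the criteria are met. Progress summaries go to the ethics committee and hospital boards (11.3), with no safety content specified. No step returns combined events to the investigators. A procedure-related SAE that is not device-related need not enter this path at all, although 6.2 names procedural risks.

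**Illustration of what pooling adds.** From the documents: at most 20 subjects (4.1, 4.4), and two centres, inferred from the two hospital boards in 10.2. Assumed, because the documents give no values: a per-subject event probability p of 2% to 20%, independent events, and a 10/10 or 15/5 split.

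The relevant case is two affected subjects in total, one at each centre. The sponsor then holds two events and each investigator has seen only one.

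- 10/10 split: [10·p·(1−p)^9]²
- 15/5 split: [15·p·(1−p)^14] × [5·p·(1−p)^4]

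At p = 10% with 10/10: 10 × 0.1 × 0.9^9 = 0.387, and 0.387² = 0.150.

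| p | 2 or more pooled, of 20 | 2 or more in at least one centre (10/10; 15/5) | Exactly one in each centre (10/10; 15/5) |
|---|---|---|---|
| 2% | 6.0% | 3.2%; 3.9% | 2.8%; 2.1% |
| 5% | 26.4% | 16.5%; 19.0% | 9.9%; 7.4% |
| 10% | 60.8% | 45.8%; 49.6% | 15.0%; 11.3% |
| 20% | 93.1% | 85.9%; 87.7% | 7.2%; 5.4% |

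The last column is the second minus the third, up to rounding. It shows direction only; it does not estimate this device's risk.

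**The case against.** The strongest reply is that this is a small open-label pilot of a CE-marked device used within its indication, by trained investigators who know their own patients. Section 1.2 calls the rate of serious complications with spinal cord stimulation low, 6.2 classes the gravest events as very rare, and 10.4 attributes non-use in this group to reimbursement, not safety. Section 7.7 can be read as ordinary clinical judgement. Much of this stands: it is why no board is called for and why the wording on routine use is a weak conflict. But licensing does not make surgery that results from enrolment observational. The category definitions in the scheme cited by 8.5 are not visible, so the documents cannot show that it was misapplied, only that the stated grounds disagree with other sections.

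Three stronger readings are tempting and not supported.

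- A reader might infer that nobody who decides ever sees pooled events. The plan is silent; it does not deny investigators pooled data. The external guidance and sponsor procedures invoked in 8.1 may require feedback that cannot be seen here.
- A reader might infer that 7.7 is the only safeguard left. There are also withdrawal for urgent medical reasons (7.4), sponsor review (8.1), follow-up of reported events (8.4) and progress reports (11.3).
- A reader might compute the chance of three or more pooled events with at most two at each centre: 25% at an assumed 20% rate and a 10/10 split. In every such case one centre has already seen exactly 2 in 10, so this is not evidence of a missed signal. Nor is the one-sided 95% upper limit of 13.9% for zero events in 20 (1 − 0.05^(1/20)): it applies to any study of that size, and pooling does not change it.

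**Conclusion.** The point holds as an internal inconsistency and a gap in documentation. The conflict between 8.5 and the Summary, 3, 7.2 and 10.4 over why subjects are implanted rests on the text alone. So does the absence of any criterion in 7.7, and of any described link from 8.1 to 7.7. That sponsor review is limited to reported device-related events judged against regulatory incident criteria.

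The practical size is modest and depends on assumptions. Over the rates and splits tried, the situation in which pooling would change what an investigator sees has a probability of about 2% to 15%. Two centres is an inference. The documents do not show that a signal would be missed or that the risk class is wrong. The change is worth making because it is cheap and concerns subjects' safety; it does not bear on the primary efficacy estimate.

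**What to change.** - **8.5:** reconcile the stated grounds with 10.4, the Summary, 3 and 7.2, and redo the risk classification on those facts. Check the observational label where it recurs (Summary, 3, 6.4, 7.2).
- **8.1:** require reporting of procedure-related as well as device-related SAEs, so that the cumulative count is complete.
- **7.7:** state that after each such SAE the sponsor's existing reviewer sends all investigators and the ethics committee a cumulative table pooled over centres. State that the investigators review it jointly before further enrolment and before pending implants in subjects already enrolled. Any review trigger should be set in advance by the sponsor and investigators; none is proposed here.

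No DSMB or additional staff is needed. The cost is an amendment to the wording, a little more reporting work and possibly a short pause.

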8 SAFETY REPORTING

8.1 Applicable local laws and regulations

For the reporting of events in this trial, applicable international standards and guidance documents for CE marked products will be followed (AIMDD, MEDDEV 2.12/2 rev2 and MEDDEV 2.12-1 rev 8), the applicable local laws and regulations, and the SMI/SJM internal operating procedures on complaint reporting, whichever is the most stringent.

In this regard investigators will only need to report device related Adverse Events (AE) and device related Serious Adverse Events (SAE).

Additionally, all reported device related AEs and SAEs will be reviewed internally at Spinal Modulation Inc./St. Jude Medical according to the criteria for incidents to be reported by manufacturers to competent authorities, as defined in section 5.1.1 in the MEDDEV 2.12-1 Rev 8.

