6 DESCRIPTION OF THE DEVICE

6.1 Name and description of Neurostimulator System

The Spinal Modulation Neurostimulator System consists of the following components:

- Trial Neurostimulator
- Implantable Neurostimulator
- Trial Lead Kit
- Implant Lead Kit
- Connector Cable Kit
- Tunnelling Tool Kit
- Clinical Programmer
- Patient Programmer
- Auxiliary Magnet Kit
- Programmer Charger Kit
- Programmer Carrying case
- Lead Accessories Kit
- 22 cm Small Curve Delivery Sheath Kit
- 22 cm Big Curve Delivery Sheath Kit
- Lead Extension Kit

A detailed description of the components can be found in the Physician Implant Manual, included in the packages of the components.

On 16 November 2011, BSI granted Spinal Modulation, Inc. CE mark for the Spinal Modulation Neurostimulator System for the management of chronic intractable pain (CE 567069). The system has been registered with the CIBG in the Netherlands on 24 November 2011 and will be utilised within its CE marked indication.

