8.2 Definitions

We will use the ISO14155:2011 as reference for the definitions of events.

Adverse Event (AE):

Any untoward medical occurrence, unintended disease or injury, or untoward clinical signs (including abnormal laboratory findings) in subjects, users or persons, whether or not related to the investigational device.

Serious Adverse Event (SAE):

Any AE that leads to:

- Death
- Serious deterioration in the health of the subject, that either resulted in
- A life threatening illness or injury, or
- A permanent impairment of a body structure or body function, or
- In-patient or prolonged hospitalisation, or
- Medical or surgical intervention to prevent life-threatening illness or injury or permanent impairment to a body structure or body function - foetal distress, foetal death or a congenital abnormality or birth defect

Planned hospitalization for a pre-existing condition, prolonged hospitalization as a result of a revision procedure, which is allowed in the protocol or a procedure required by the protocol, without serious deterioration in health, is not considered a serious adverse event.

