8.4 Follow-up of adverse events

All reported device related events will be followed until they have abated, or until a stable situation has been reached, unless the subject is lost to follow-up.

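### Section 8.1 makes a site's judgement that an event is device related the condition for recording it, so SAEs judged unrelated, and procedural harms on a narrow reading, can stay out of the safety data

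*Combined protocol and SAP*

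**What the plan says.** Section 8.1 names the sources that govern event reporting (the directive and guidance for CE-marked products, local law, and company complaint procedures) and applies "whichever is the most stringent". It then gives sites the practical consequence: "investigators will only need to report device related Adverse Events (AE) and device related Serious Adverse Events (SAE". The manufacturer's internal review, in the same section, covers the device-related events that were reported.

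Section 8.3 requires CRF entry for reportable events. Section 8.4 adds: "All reported device related events will be followed until they have abated, or until a stable situation has been reached", except for subjects lost to follow-up.

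On definitions, section 8.2 says "We will use the ISO14155:2011 as reference for the definitions of events". It defines an AE regardless of any relation to the device. From the SAE definition it removes, where health has not seriously deteriorated, "prolonged hospitalization as a result of a revision procedure, which is allowed in the protocol or a procedure required by the protocol". Neither 8.1 nor 8.2 says what device related means.

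Section 6.2 says "Possible risks to the subjects include both device and procedural based risks" and then lists the risks without marking which kind each is. Appendix A provides AE and SAE forms in all 10 columns, including Trial Procedure, Final Implant and Revision, marked for use only if needed.

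**The concern.** Relatedness is normally an attribute recorded for each event, so that it can be tabulated and, if necessary, challenged. Here it decides whether the event has to be recorded at all. An event on the wrong side of that judgement need not reach a CRF, so nobody can revisit the judgement from the study data.

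This matters in this study for three reasons. The Summary lists safety among the data the study is designed to collect. The therapy is delivered by invasive procedures in two stages (section 3), and leads may be placed a second time at the implant (section 7.3). Finally, section 8.5 dispenses with a DSMB and section 7.7 rests early termination on the investigators' view of risk, so no separate body within the study would look at events that were not reported. If procedural harms or serious events were filtered out, the safety results would understate the harms of the therapy as delivered.

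**Working it through.** The plan gives no figure to reproduce. The check sets the provisions side by side and then counts what can be counted.

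1. **Reporting, recording and follow-up.** Section 8.1 limits the duty to report to device-related events. Section 8.3 attaches CRF entry to reportable events. Section 8.4 attaches follow-up to reported device-related events. All three therefore depend on one judgement made at the site.

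2. **SAEs judged unrelated.** Section 8.2 defines events without regard to cause, while section 8.1 asks only for the related ones. An SAE that the site judges unrelated falls outside the written duty, whether or not procedural harms count as device related.

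3. **Procedural harms.** No visible sentence says whether harms of lead placement, tunnelling, implant, revision or explant are device related.
   - *For the broad reading:* section 6.1 lists leads, delivery sheaths and the "Tunnelling Tool Kit" as components of the System. Section 6.2 introduces its risks as those of the System and places items such as "Bleeding (where the needle has been inserted" and infection in the same list as lead migration. The hospitalisation exclusion in section 8.2 would be largely unnecessary if procedural events were already out of scope. Appendix A has event forms in the procedure columns.
   - *For the narrow reading:* section 6.2 names device and procedural risks as two kinds, and section 8.1 names only one of them.
   - *Result:* the balance favours the broad reading, but it has to be inferred. The section 8.2 exclusion concerns seriousness, not relatedness, and a form marked only if needed makes capture possible without requiring it. Two sites could reasonably decide differently.

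4. **What can be counted.**
   - Section 6.2 lists 17 most common risks. Three are placed by their own wording at the needle or injection site: pain, bleeding and a collection of serous fluid. The protocol itself expects harms of this kind.
   - Enrolment is at most 20, and subjects already enrolled continue after the 15th implant (section 4.1). Maximum planned procedures: 20 trial lead placements + 20 implants = 40. If 20 enrol and 15 are implanted: 20 + 15 = 35. Revisions and explants are additional.

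5. **What cannot be counted.** The documents give neither an event rate nor the share of events that sites would judge not device related. The number of events lost cannot be derived. The 35 to 40 procedures measure exposure, not loss.

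**The case against.** The strongest defence is that device-related reporting is a deliberate choice. Section 8.1 ties it to the rules for CE-marked products used within their indication, and it delegates detail to an ISO standard, to regulatory guidance and to a most-stringent clause. Those sources may define relatedness or widen the duty, and blacked-out parts of the objectives, the assessments and Appendix A might too. The AE and SAE forms themselves are not shown, so a relatedness field may already exist. All of this stands as a limit on what can be claimed. It does not remove the point, because the sentence addressed to sites names device-related events only and tells them of no wider duty.

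Three stronger readings are tempting, and the documents do not support them.

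- *The protocol excludes procedural harms.* It does not say so, and most of the relevant text points the other way.
- *The all-cause AE definition contradicts the reporting rule.* It does not: a definition and a reporting scope do different jobs.
- *Filtered events would leave no trace.* Appendix A also schedules Revision and Trial Exit forms, and section 10.3 promises careful monitoring of subjects. Only the duty to record an event as an AE or SAE is shown to be missing.

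It is also fair to say that safety appears in the Summary's description of the design, not among the visible objectives in section 2, some of which are redacted.

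**Conclusion.** The point holds as a cheap improvement. As written, sections 8.1, 8.3 and 8.4 allow an SAE judged unrelated to go unrecorded. They also allow a procedural harm to go unrecorded where a site reads device related narrowly. The first follows directly from the text. The second depends on a reading that the documents make less likely but do not rule out. The consequence is possible understatement of harms, and a relatedness judgement that cannot be re-examined, over at most 40 planned procedures plus any revision or explant. A reader might infer that the safety results will be biased by some known amount, or that a reporting standard has been breached. Neither can be shown: the documents contain no event rates, and the external standards are not available here. The conclusion assumes that no redacted text or unseen form already widens the duty.

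**What to change.** Change section 8.1 so that investigators record all SAEs, and all AEs related or possibly related to the device, the stimulation or a study procedure, naming trial lead placement, tunnelling, implant, revision and explant. Record relatedness (device, procedure, stimulation, unrelated) as a CRF field, if one is not already there, in place of using it as a condition of entry. Align section 8.4 with the same scope. Add to section 9 a summary of reported events by relatedness, since the visible analysis text describes no safety summary.

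The cost is protocol wording and at most one CRF field, on forms already scheduled in every column of Appendix A. The downside is slightly more site reporting for at most 20 subjects, beyond the post-market minimum that the sponsor chose. If the sponsor keeps that minimum, one sentence in section 8.1 or 8.2 stating whether device related includes the implant and revision procedures would settle the procedural question. It would leave unrelated SAEs outside the duty, and any safety summary should then say so.
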